## Protocol Change History

Version	Section(s)	Page(s)	Description of Change(s)	Rationale for Change(s)
1.0	N/A	N/A	Original	N/A
2.0	Synopsis and 8.1 Inclusion Criteria	2,13	Change Corneal Astigmatism criteria to be " Predicted postoperative corneal astigmatism of less than 1.00 D in both eyes"	To align with indications for use.
2.0	Synopsis and 8.2 Exclusion Criteria	3,14	Reference guttata for endothelial dystrophy	To clarify with an example of a sign of endothelial dystrophy.
2.0	9.1 Investigator Qualifications	15	Change requirement of established Symphony A-Constant to ZCB00 A-Constant	The control IOL in this study is ZCB00 thus surgeon needs to have an established A-Constant for the ZCB00 lens.
2.0	10.3 Keratometry	20	Add language to account for PCA in the determination of total corneal astigmatism for study qualification.	To ensure inclusion criteria are fully met.
2.0	10.3 IOL Power and Targeted Refraction	21	Add language to reflect different A-Constant for investigational vs. control lens and establish that IOL power changes will only be based on first-eye outcomes	To ensure proper calculation of IOL power for study subjects and to reduce surgeon changes intraoperatively.
2.0	10.6 Operative Procedures	23	Change astigmatism to be less than 1.00 D instead of no greater than 1.0 D.	To align with indications for use.
2.0	10.7 Postoperative Procedures (Defocus Testing) and Appendix I	27, 63	Remove two defocus increments (+0.25 D and -0.25 D) in defocus testing	The optical design is to extend depth of focus in the -2.0 to -4.0 D range so this finer defocus testing around 0.0 D is not needed.
2.0	20.1 Analysis Population	44,45	Add mean BCDVA safety endpoint to sensitivity analyses, add cumulative adverse events to safety population	Per FDA Study Considerations in Approval letter dated 30Mar2018 resulting in SAP amendment to clarify planned analyses.
2.0	Appendix A	52	Remove pupil size measurement at 1-Month visit	Correction as no testing is done at 1 Month for which pupil size stratification may be performed. All testing is photopic visual acuity only.
2.0	Appendix B	53	Add "as requested" and "as necessary" for equipment that is optional	Clarification
2.0	footer	all	Update footer to 2.0	New version
3.0	10.7 Postoperative Procedures (Questionnaires)	29, 30	Add "v2" to PRSIQ and PRVSQ, change number of symptoms to seven from eight due to removal of streaks of light	New testing of PRVSQ combined streaks of light into starbursts, resulting in v2 or PRVSQ.

3.0	10.9 Unscheduled Visits	32	Change number of symptoms to seven from eight due to removal of streaks of light	New testing of PRVSQ combined streaks of light into starbursts, resulting in v2 or PRVSQ.
3.0	Appendix M		Replace PRVSQ with PRVSQv2	Update with new PRVSQ that has undergone additional validation testing
3.0	Appendix N		Replace PRSIQ with PRSIQv2	Update with new PRSIQ that has undergone additional validation testing
3.0	footer	all	Update footer to 3.0	New version
4.0	Table of Contents	ii-iv	Renumbered pages	Updates due to changes
4.0	Synopsis, 3. Clinical Hypothesis	1, 4, 6	Changed decreased spectacle wear to increased spectacle independence	Update with PRSIQv2 validation work to use composite dichotomous score for overall spectacle independence as secondary effectiveness endpoint
4.0	Synopsis	5	Remove overall spectacle independence secondary effectiveness endpoint from mITT analysis population	Composite dichotomous scoring algorithm does not impute for missing data
4.0	6.2 Secondary Effectiveness Endpoint	8	
Replace “Overall Spectacle Wear” with “Overall Spectacle Independence”
 
Replace “do not wear spectacles...” with “are spectacle independent” and update definition of PRO instrument assessment.
 
Replace clinical significance of “50% of subjects will report wearing glasses “None of the time”...” with “The proportion of Model ZHR00 subjects who are spectacle independent will be at least 25 percentage points higher than that for the control group”
	Update with PRSIQv2 scoring algorithm to use composite dichotomous score for overall spectacle independence as secondary effectiveness endpoint instead of overall spectacle wear
4.0	20.1 Analysis Population	44, 45	Reworded to clearly define that PRSIQv2 data will be analyzed in Safety Population and Per Protocol analyses and will not be imputed for mITT analyses.	PRSIQv2 scoring algorithm requires complete data for composite dichotomous score and specifies no imputation for missing values should be used.
4.0	20.2 Secondary Effectiveness Endpoints Overall Spectacle Independence	47, 48	
Replace the secondary effectiveness endpoint of Overall Spectacle Wear via Binocular Questionnaire with Overall Spectacle Independence, including all questions and conditions that are included in the composite dichotomous score.
 
Replace clinical significance of “50% of subjects will report wearing glasses “None of the time”...” with “The proportion
	Update with PRSIQv2 validation work to use composite dichotomous score for overall spectacle independence as secondary effectiveness endpoint.

			of Model ZHR00 subjects who are spectacle independent will be at least 25 percentage points higher than that for the control group" Remove logistic regression from data analysis	No imputation will be done on PRSIQv2 missing data therefore only Fisher's exact test will be used.
4.0	Appendix A	52	Added shading to Manifest refraction examination	Correction as this is an examination that is to be conducted by a masked examiner
4.0	footer	all	Update footer to 4.0	New version

## 1. SYNOPSIS

**PROTOCOL:** Clinical Investigation of the Safety and Effectiveness of the Next-Generation TECNIS® Symfony® Intraocular Lens, Model ZHR00  
Protocol Number: SUR-IOL-652-2001

### STUDY TREATMENTS:

Investigational Lens:

- Next-Generation TECNIS Symfony IOL, Model ZHR00

Control Lens:

- TECNIS Monofocal IOL Model ZCB00 (Johnson & Johnson Surgical Vision, Inc., Santa Ana, CA), commercially available

**STUDY OBJECTIVE:** The purpose of this clinical trial is to evaluate the safety and effectiveness of the Next-Generation TECNIS Symfony IOL, Model ZHR00.

**CLINICAL HYPOTHESIS:** The Next-Generation TECNIS Symfony IOL, Model ZHR00, will provide improved monocular, distance-corrected intermediate visual acuity (at 66 cm) and distance-corrected near visual acuity near (at 40 cm), as well as increased depth of focus at 0.2 LogMAR and increased spectacle independence compared to the control IOL, TECNIS Model ZCB00.  
Complication and adverse event rates associated with the Next-Generation IOL will be within the rates for posterior chamber IOLs referenced in ISO 11979-7:2006/ Amd 1:2012(E).

### OVERALL STUDY DESIGN:

**Structure:** Prospective, multicenter, randomized, bilateral subject/evaluator-masked clinical trial

**Number of sites:** Up to 10 sites in the United States

**Duration:** 6 months postoperative follow-up

**Administration:** Surgeons will perform routine, small-incision, cataract surgery and implant the study lenses using a sponsor-recommended implantation system. Refractive target outcomes will be emmetropia for both eyes.

**Visit Schedule:** Subjects will be bilaterally implanted with the same lens type; the second eye is to be implanted within 1 month of the first-eye surgery.

All subjects will undergo 10 scheduled visits: Preoperative for both eyes; Operative, 1-day, 1-week and 1-month visits for each eye; and a 6-month visit for both eyes.

### **STUDY POPULATION CHARACTERISTICS:**

**Condition:** Bilateral cataracts with otherwise-healthy eyes

**Number of Subjects:** Up to 264 subjects will be enrolled to achieve approximately 110 randomized and bilaterally-implanted subjects in each lens group.

Each site should enroll at least 20 subjects, and no site may enroll more than 25% of the enrollment total.

#### **Inclusion Criteria (all criteria apply to each study eye):**

- Minimum 22 years of age
- Bilateral cataracts for which posterior chamber IOL implantation has been planned
- Preoperative best-corrected distance visual acuity (BCDVA) of 20/40 Snellen or worse with or without a glare source
- Potential for postoperative BCDVA of 20/30 Snellen or better
- Corneal astigmatism:
  - Normal corneal topography
  - Predicted postoperative corneal astigmatism of less than 1.00 D in both eyes
- Clear intraocular media other than cataract in each eye
- Availability, willingness and sufficient cognitive awareness to comply with examination procedures and study visits
- Signed informed consent and HIPAA authorization or equivalent documentation necessary to comply with applicable privacy laws pertaining to medical treatment in the governing countries
- Ability to understand and respond to a questionnaire in English

#### **Exclusion Criteria (all criteria apply to each study eye):**

- Requiring an intraocular lens power outside the available range of +14.0 D to +26.0 D

- Any clinically-significant pupil abnormalities (non-reactive, fixed pupils, or abnormally-shaped pupils)
- Irregular corneal astigmatism
- Inability to focus or fixate for prolonged periods of time (e.g., due to strabismus, nystagmus, etc.)
- Prior corneal refractive (LASIK, LASEK, RK, PRK, etc.) or intraocular surgery, including prophylactic peripheral iridotomies and peripheral laser retinal repairs
- Corneal abnormalities such as stromal, epithelial or endothelial dystrophies (e.g., any observed guttata) that are predicted to cause visual acuity losses to a level worse than 20/30 Snellen during the study
- Inability to achieve keratometric stability for contact lens wearers
- Recent ocular trauma or ocular surgery that is not resolved/stable or may affect visual outcomes or increase risk to the subject
- Subjects with diagnosed degenerative visual disorders (e.g., macular degeneration or other retinal disorders) that are predicted to cause visual acuity losses to a level of 20/30 Snellen or worse during the study
- Subjects with conditions associated with increased risk of zonular rupture, including capsular or zonular abnormalities that may lead to IOL decentration or tilt, such as pseudoexfoliation, trauma, or posterior capsule defects
- Use of systemic or ocular medications that may affect vision
- Prior, current, or anticipated use during the course of the 6-month study of tamsulosin or silodosin (e.g., Flomax, Flomaxtra, Rapaflo) that may, in the opinion of the investigator, confound the outcome or increase the risk to the subject (e.g., poor dilation or a lack of adequate iris structure to perform standard cataract surgery)
- Poorly-controlled diabetes
- Acute, chronic, or uncontrolled systemic or ocular disease or illness that, in the opinion of the investigator, would increase the operative risk or confound the outcome(s) of the study (e.g., immunocompromised, connective tissue disease, suspected glaucoma, glaucomatous changes in the fundus or visual field, ocular inflammation, etc.). Note: controlled ocular hypertension without glaucomatous changes (optic nerve cupping and visual field loss) is acceptable.
- Known ocular disease or pathology that, in the opinion of the investigator,
  - may affect visual acuity
  - may require surgical intervention during the course of the study (macular degeneration, cystoid macular edema, diabetic retinopathy, uncontrolled glaucoma, etc.)
  - may be expected to require retinal laser treatment or other surgical intervention during the course of the study (macular degeneration, cystoid macular edema, diabetic retinopathy, etc.)
- Patient is pregnant, plans to become pregnant, is lactating or has another condition associated with the fluctuation of hormones that could lead to refractive changes
- Concurrent participation or participation within 60 days prior to preoperative visit in any other clinical trial
- Desire for monovision correction

**EVALUATION CRITERIA:**

The purpose of this clinical study is to evaluate the safety and effectiveness of the Next-Generation TECNIS Symphony IOL. The primary effectiveness endpoints are:

- mean monocular distance-corrected intermediate visual acuity under photopic conditions at 66 cm
- monocular distance-corrected depth of focus under photopic conditions.

The secondary effectiveness endpoints are:

- mean monocular, distance-corrected near visual acuity at 40 cm under photopic conditions
- overall spectacle independence

The safety endpoints are:

- monocular photopic, best-corrected distance visual acuity non-inferior to control
- adverse event rates versus ISO 11979-7:2006/ Amd.1:2012(E) Safety and Performance Endpoint (SPE) rates, monocular contrast sensitivity and visual symptoms via PRO questionnaire. Adverse events will include any lens-related secondary surgical intervention due to optical issues causing visual symptoms.
- contrast sensitivity
- visual symptoms as reported via PRO instrument

Other endpoints include:

- Monocular BCDVA percent 20/40 or better vs. ISO SPE rate
- Binocular best-corrected distance depth of focus
- Binocular UCDVA, UCIVA, and UCNVA
- Monocular UCDVA, UCIVA, and UCNVA
- Monocular, first-eye, low-contrast DCIVA and BCIVA (10%)
- Medical findings/complications
- Lens findings/complications
- Fundus visualization
- Residual refractive error
- Ocular/visual symptoms (non-directed responses as obtained from the open-ended question “Are you having any difficulties with your eyes or vision?”)
- Subject satisfaction and other questionnaire responses

#### **DATA ANALYSIS:**

The investigational TECNIS Model ZHR00 IOL will be compared to the TECNIS Model ZCB00 control IOL. For the primary effectiveness endpoints of monocular distance-corrected intermediate visual acuity and both secondary effectiveness endpoints at 6 months, comparisons between the Model ZHR00 group vs. the Model ZCB00 control group will be performed using one-sided, two-sample t-tests with an alpha of 0.025.

For the safety endpoints, monocular BCDVA will be compared to the control lens using non-inferiority approach and evaluated using the lower limit of the two-sided 90%

confidence interval. Adverse event rate of the Model ZHR00 IOL will be compared to the ISO grid value using one-sided exact tests with an alpha of 0.05. For contrast sensitivity, descriptive statistics (mean, standard deviation, median, minimum, maximum and 90% confidence interval) will be presented by IOL group. For ocular visual symptoms via questionnaire, frequency and proportion of each response will be presented by IOL group.

The primary analysis population for primary DCIVA and secondary DCNVA effectiveness endpoints will be the mITT. The primary analysis population for primary defocus curve effectiveness endpoint, secondary overall spectacle independence effectiveness endpoint, all safety endpoints and other endpoints will be SP. Please see a detailed description of the analysis populations in Section 20.1. The key study timeframe for all endpoints will be the 6-month postoperative visit, although data will be reviewed at other time points as well. In general, descriptive statistics will be reported for visual acuity and refractive data. The frequency and proportion will be reported for adverse events, medical findings, lens findings, and ocular visual symptoms, as well as questionnaire data.

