#### RATES OF ADVERSE EVENTS VS. ISO SPE RATES

Rates of adverse events as determined by ISO 11979-1 will be reported through 6 months. The frequency and proportion of first eyes and second eyes with these events will be reported over time by IOL group. Statistical comparisons to ISO SPE rates will be based on first-eye data; adverse event rates for the Model ZHR00 first eyes will be compared to the ISO SPE rates using a one-sided, exact test based on the binomial distribution. The null hypothesis is that the AE rate for the Model ZHR00 eyes is lower than or equal to the ISO rate, and the alternative hypothesis is that the AE rate for ZHR00 eyes is greater than the ISO rate. This criterion will be used for all ISO SPE rates, including secondary surgical interventions (SSI). In addition, rates for lens-related SSI due to optical issues causing visual symptoms will be presented with descriptive statistics.

$$H_0: p_t \leq p_i$$

$$H_1: p_t > p_i$$

where

$p_t$  = proportion of Model ZHR00 investigational lens eyes with the AE

$p_i$  = proportion of eyes reported in ISO SPE rates with the AE

Reject the null hypothesis if one-sided p-value < 0.025.

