The safety population will consist of all eyes and subjects implanted with either a test or control IOL(s) and with data available at the time of analysis (i.e., no data imputation). Reporting of cumulative complications and cumulative adverse event (occurring at any time postoperative either at standard visits or interim visits) will include data from all study eyes implanted. Thus, all adverse events at any postoperative visit (including standard or interim visit) will be reported unless it is results at a given visit (i.e., 6 months). For all safety endpoints, only the safety population will be used. For BCDVA, a best-case population will also be used, consisting of eyes in the safety population without any clinically-relevant preoperative ocular pathologies or macular degeneration detected at any time.

For the primary DCIVA, and secondary DCNVA, the mITT, PP and safety populations will be used for data reporting. For the defocus curve primary endpoint and overall spectacle independence secondary endpoint, only safety and PP populations will be used for data reporting. For safety endpoints and other endpoints, only the safety population will be used. The primary analysis will be based on first-eye data, unless stated otherwise. However, select data such as some visual acuity variables will also be reported separately for second eyes as supportive data only. Binocular data will be reported for those who are implanted with the same (test or control) IOL in both eyes. For demographics/enrollment/accountability data will also be reported for all randomized subjects whether an IOL was implanted or not with group assignment based on the randomization. Appendix I lists the analysis tables including the endpoints and the populations used to report the results.

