## **2.3 DATA CONVENTIONS**

Descriptive statistics will typically include sample size (N), mean, standard deviation (SD), median, minimum (Min.), and maximum (Max.) as appropriate for continuous variables. For categorical data, the frequency and proportion will be computed.

For continuous variables, statistical tests assuming normality will generally be used. However the data will be reviewed to evaluate whether the normality assumption is appropriate. If it is found not to be appropriate, either an appropriate transformation of the data (i.e., logarithmic) may be used or the corresponding non-parametric tests may

be used. Deviations from the proposed statistical guidelines will be substantiated by sound statistical rationale. For categorical data, Fisher's exact test will be used for comparison between IOL groups. Comparisons for ordinal data will be done using the Wilcoxon rank-sum test.

Unless otherwise indicated, alpha will be set to 0.05 for two-sided statistical testing with alpha set to 0.025 for one-sided testing. See Section 2.5 Multiplicity Adjustment below for the primary and secondary endpoints related to product claims.

For visual acuity data, letter scores will be converted to LogMAR prior to analysis. Formulas used for visual acuity analysis are included in Appendix II. For refractive data, all values will be converted to plus cylinder with sphere adjusted for infinity. Formulas used for refractive data are also included in Appendix II.

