## **2.5 MULTIPLICITY ADJUSTMENT**

No multiplicity adjustment is planned for the primary effectiveness endpoints of DCIVA and defocus since only the DCIVA endpoint requires hypothesis testing. One-sided testing with alpha level of 0.025 is planned for this endpoint. No multiplicity adjustment is planned for the safety endpoints.

Due to multiple secondary endpoints, a closed-form hierarchical approach will be used to evaluate statistical significance. Secondary endpoints will be tested in the following order:

1. Monocular distance corrected near visual acuity at 40cm
2. Overall spectacle independence

Since one-sided testing will be performed, an alpha level of 0.025 will be used. The hierarchical approach for p-value adjustment is based on a statistically significant p-value for each test. Therefore, if other clinical criteria associated with the endpoint are not met but statistical significance is achieved, testing will proceed hierarchically to the following endpoint.

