## **6.4 MEDICAL/LENS FINDINGS**

Rates of postoperative medical and lens findings will be tabulated with the frequency and proportion of eyes with these events reported over time by IOL group. As mentioned above in Section 5.3.2 Safety Endpoints: Rates of Adverse Events, medical complication rates listed in ISO-11979 will be compared to the ISO SPE rates for ZHR00 first eyes using a one-sided, exact test based on the binomial distribution. The null hypothesis is that the study rate for ZHR00 eyes is lower than or equal to the ISO rate and the alternative hypothesis is that the rate for ZHR00 eyes is greater than the ISO rate.

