## **7.3 MONOCULAR, BEST CORRECTED DISTANCE VISUAL ACUITY (BCDVA)**

For monocular BCDVA, there is over 90% power to detect a non-inferiority margin of 1 line between the test and control IOL groups (assumes one-sided alpha=0.05, no difference in mean BCDVA between IOL groups and a standard deviation of 1.2) with 100 subjects in each group.

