## **7.4 SAFETY ENDPOINTS COMPARED TO ISO SPE RATES**

For the percent of first eyes achieving 20/40 or better BCDVA compared to ISO SPE rates and for adverse event rates compared to ISO SPE rates, the sample size of 100 test subjects was chosen based on revision 07 of the draft ANSI Z80.35 standard that specifies a minimum of 100 test subjects when the investigational lens is a modification of an approved monofocal parent. This document also specifies that there should be 100 subjects in the control arm. To achieve 100 evaluable subjects in each IOL group and allowing for screen failures and drop outs, it was determined that 264 subjects needed to be enrolled. The following calculations were performed to determine the overall number of subjects in the study. The number of randomized subjects needed (assuming a 10% drop-out):  $200/0.9=222.2$ . This was rounded to 224 so there would be an even number for the two IOL groups. The number of enrolled subjects needed (assuming a 15% screen failure rate):  $224/0.85=263.5$ . This was rounded to 264.

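### The adverse-event test against ISO rates has a one-sided alpha of 0.05 in the Synopsis and 0.025 in Protocol 20.2 and SAP 5.3.2

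*Protocol*

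**What the plan says.** The safety endpoint is the rate of each adverse event in ZHR00 first eyes, tested against a fixed ISO rate.

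- **Protocol Synopsis, Data Analysis:** the rate "will be compared to the ISO grid value using one-sided exact tests with an alpha of 0.05".
- **Protocol 20.2, Rates of Adverse Events vs. ISO SPE Rates:** a one-sided exact binomial test with H0 that the ZHR00 rate does not exceed the ISO rate and H1 that it does. The rule is "Reject the null hypothesis if one-sided p-value < 0.025".
- **SAP 5.3.2:** the same test, hypotheses and 0.025 rule as Protocol 20.2.
- **SAP 2.3:** unless otherwise indicated, "alpha set to 0.025 for one-sided testing".
- **SAP 6.4:** applies the test to medical complications and gives no alpha of its own. It refers back ("As mentioned above in Section 5.3.2 Safety Endpoints: Rates of Adverse Events") and so inherits 0.025.
- **SAP 2.5:** "No multiplicity adjustment is planned for the safety endpoints".
- **SAP 7.4:** for this comparison, "the sample size of 100 test subjects was chosen based on revision 07 of the draft ANSI Z80.35 standard". It gives no alpha.
- **SAP 7.3:** the power statement for another safety endpoint, mean BCDVA, "assumes one-sided alpha=0.05, no difference in mean BCDVA between IOL groups".

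**The concern.** All three statements of the test call it one-sided, so the twofold difference is not a one-sided against two-sided way of writing the same level. The comparator is also the same: the Task Force statement in Protocol Appendix Q explains that Grid and SPE are two names for these benchmarks.

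The documents offer no explanation. With no multiplicity adjustment for safety endpoints, 0.025 is not an adjusted 0.05. The change histories of both documents record no change to this alpha. The Synopsis refers to Section 20.1 only for analysis populations. One-sided 0.05 is in use for mean BCDVA, so the Synopsis value cannot be set aside as an obvious typing error.

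Rejecting H0 is the safety signal, so the stricter alpha makes the signal harder to raise. With two values on paper, a borderline count could be read either way once the data are known.

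**Working it through.** **1. The plan's own figure.** The only calculation given for this comparison is the enrolment total in SAP 7.4: 200/0.9 = 222.2, rounded to 224 randomized; 224/0.85 = 263.5, rounded to 264 enrolled. It reproduces exactly. No alpha enters it, so it cannot show which level was intended.

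**2. Inputs for the comparison.**
- Alphas: 0.05 (Synopsis) and 0.025 (Protocol 20.2, SAP 5.3.2).
- n = 100 ZHR00 first eyes: the evaluable target.
- n = 112: 224/2, from SAP 1. The larger number is relevant because SAP 2.1 says that reporting of cumulative adverse events "will include data from all study eyes implanted".
- n = 110: the Protocol's planned number implanted per group.
- ISO rate p0: not in the documents. I assume 0.1% to 5%; no actual ISO category can be placed in that range from the documents.

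**3. Formula.** The cut-off c is the smallest count with P(X ≥ c) < alpha, where X is binomial(n, p0) and P(X ≥ c) = Σ C(n,k) p0^k (1 − p0)^(n−k) for k = c to n. The false-flag chance is P(X ≥ c) at p0. The chance of flagging a doubled rate is P(X ≥ c) at 2·p0.

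**4. Cut-offs at selected assumed rates (events needed at 0.05 / at 0.025).**

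| Assumed ISO rate | n = 100 | n = 110 | n = 112 |
|---|---|---|---|
| 0.5% | 3 / 3 | 3 / 3 | 3 / 3 |
| 1% | 4 / 4 | 4 / 5 | 4 / 5 |
| 2% | 6 / 6 | 6 / 6 | 6 / 7 |
| 3% | 7 / 8 | 7 / 8 | 8 / 8 |

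Tail probabilities where the cut-offs differ:
- n = 100, 3%: P(X ≥ 7) = 0.0312, P(X ≥ 8) = 0.0106.
- n = 110, 1%: P(X ≥ 4) = 0.02504, P(X ≥ 5) = 0.0051.
- n = 110, 3%: P(X ≥ 7) = 0.0483, P(X ≥ 8) = 0.0181.
- n = 112, 1%: P(X ≥ 4) = 0.0265, P(X ≥ 5) = 0.0055.
- n = 112, 2%: P(X ≥ 6) = 0.0255, P(X ≥ 7) = 0.0075.

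**5. Whole assumed range** (0.10% to 5.00% in steps of 0.01 percentage points, 491 rates, equal weight; pairs are alpha 0.05 / 0.025).

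| | n = 100 | n = 110 | n = 112 |
|---|---|---|---|
| Largest difference in cut-off | 1 event | 1 event | 1 event |
| Share of rates where cut-offs differ | 62% | 66% | 64% |
| Mean chance of flagging a doubled rate | 33.4% / 24.9% | 36.0% / 27.0% | 36.3% / 27.6% |
| Mean false-flag chance per category | 2.95% / 1.44% | 3.04% / 1.46% | 3.02% / 1.48% |

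**6. Sensitivity to the assumed range.** Keeping only 0.1% to 1% at n = 100, the doubled-rate figures fall to 10.7% / 6.9% and the false-flag figures to 2.2% / 1.1%.

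**The case against.** The best defence is that the operative texts leave little room for doubt. Only Protocol 20.2 and SAP 5.3.2 set out hypotheses and a rejection rule, and they agree. SAP 2.3 backs them, and SAP 1 presents the SAP as the statement of methods to be implemented. An analyst working from the SAP would use 0.025. The same Synopsis paragraph also names the wrong test for spectacle independence, which suggests a loosely edited summary more than a rival rule. This stands, and it is why the point is minor. It does not remove the conflict: a SAP default is not a precedence clause over the Protocol Synopsis.

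The consequence is also limited. Unlike BCDVA, this endpoint has no stated success criterion. Event frequencies are reported whatever the alpha, and the Protocol's safety monitoring and termination sections do not refer to this p-value. What could change is whether a category is labelled as above the ISO rate, and by one event at most. That also stands.

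Finally, the averages rest on assumed rates and an assumed doubling, and they depend on the 5% upper end, as step 6 shows. Some single-rate examples are knife-edge: the 2% difference at n = 112 disappears at n = 110, where 6 events give p = 0.0236 and satisfy both rules. The averages should be read as an order of magnitude, not as properties of the trial. The conflict in the text does not depend on them.

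**Conclusion.** The concern holds as a minor inconsistency: one safety test carries two decision thresholds. The weight of the text favours 0.025 and makes the Synopsis sentence the one out of line.

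For an event category whose ISO rate falls where the cut-offs differ, one particular count would be called an excess under the Synopsis and not under Protocol 20.2 and the SAP. Under the assumed rates, moving from 0.05 to 0.025 roughly halves the false-flag chance per category and lowers the average chance of flagging a doubled rate by about 8 to 9 percentage points. The finding of a conflict rests on the text alone. Only its size rests on the assumed ISO rates, the equal weighting and the choice of n.

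**What to change.** State one alpha everywhere before database lock.

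- **Simplest:** change the Synopsis figure to 0.025, in line with Protocol 20.2, SAP 5.3.2 and SAP 2.3. This is one number, with no effect on sample size, data collection or SAP text.
- **If the sponsor intends 0.05:** change Protocol 20.2 and SAP 5.3.2 together (SAP 6.4 then follows) and accept about double the false-flag chance per category, on average 1.4% rising to 3.0% at n = 100 over the assumed rates.

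In the same Synopsis paragraph, replace the two-sample t-test for overall spectacle independence with Fisher's exact test, which Protocol 20.2 and SAP 5.2.2 already specify. That is a separate wording slip and costs one test name.

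Optionally, and not as the correction of an error, report an exact upper confidence limit beside each ISO rate, so that the reader sees what excess the data can exclude.
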